9.1.6. Description of study procedures

Demographic and anthropometric data collection

Demographic data include date of birth, age (number of full years at the time of participation in the study), gender and race. Anthropometric data include weight and height.

Medical history collection

The medical history data includes a description of the underlying disease, including the duration and effect of previously received therapy, a description of previous and concurrent diseases. In addition, information about concomitant therapy shall be collected: INN, trade name, strength, presentation, single and daily dose, date of therapy initiation and termination.

Physical examination

Physical examination includes an examination of the following organs and systems:

- Skin, hair, nails
- Endocrine system
- Cardiovascular system
- Respiratory system, state of nasal passages, character of discharge
- Gastrointestinal tract, including oral examination using a spatula and flashlight
- Nervous system
- Musculoskeletal system
- Reproductive system
- Urinary system

Measurement of vital signs

Measurement of HR, RR shall be performed by qualified medical personnel in accordance with the standards adopted at the study site.

The study is conducted as part of the safety assessment of study subjects.

Body temperature measurement.

It is conducted at screening visits, Visit 1, 2 and 3 by medical personnel, and at home by parents/adoptive patients.

Algorithm for measuring body temperature:

1. Wash your hands with warm water and soap
2. Inspect the armpit, and wipe it dry

3. Take a thermometer and shake off mercury below 35 °C
4. Position the thermometer in the armpit so that the measuring tank is in contact with the body from all sides
5. Measure the temperature for 10 min
6. Pay attention to between the body and the thermometer was no linen
7. Remove the thermometer and record the digital data
8. Shake the thermometer

Parents/adoptive parents should be instructed on how to conduct thermometry at Screening.

ECG

It shall be conducted at suspicion on cardiovascular disease. At least an hour before the procedure, it is necessary to exclude the outdoor games and emotional stress of the child. No less than 1.5 hours shall pass after the meal. In young children, special electrodes are used, which are tightly fixed on the skin without damaging it. Record at least 10–15 cardiac cycles, and if they are suspicion on of arrhythmia, there may be more cycles.

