11.1 Methods and terms of analysis safety parameters recording

The presence of adverse events is assessed according to the patients' complaints, as well as according to the physical examination and the results of laboratory and instrumental examination. Investigators are responsible for identifying, providing necessary medical care, documenting and reporting cases that fall within the definition of AE and SLEEP.

For safety assessment, the following laboratory parameters are determined according to the schedule of Visits (Visit 0 (Screening), Visit 3 (Day 8 ± 1)):

- Clinical blood test;
- Common urine analysis.

Laboratory deviations

Any clinically significant abnormalities in the clinical blood count, clinical urine analysis will be evaluated by the Investigator. In case of significant deviations of laboratory parameters on Visit 3 (day 8 ± 1) in comparison with the initial parameters at Visit 0 (screening), it is necessary to conduct additional laboratory monitoring before normalizing or determining the cause of the deviation.

Any additional laboratory control is carried out by the Investigator's decision. Any clinically significant laboratory deviation shall be documented as AE in the patient's medical record and in the CRF unless the deviation is due to laboratory error; in this case, a corresponding note shall be made in the primary documents.

General medical history and anamnesis morbi

General information about the medical history and anamnesis morbi is collected on the screening visit and includes:

- date of disease onset;
- previous and concurrent diseases, and surgery in the previous 6 months prior to the study inclusion;
- concomitant therapy (drug products, other treatments) and products used for 6 months prior to the study inclusion;
- smoking, alcohol and narcotic drug abuse.

Physical examination

A general physical examination is conducted on Visit 0 (Screening), Visit 1 (Day 1), Visit 2 (Day 3), Visit 3 (Day 8 ± 1). Clinically significant changes on visits - Visit 1 (Day 1), Visit 2 (Day 3), Visit 3 (Day 8 ± 1), absent on Visit 0 (Screening) are regarded and documented as AE in the patient's medical record and in the CRF.

Major vital signs

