12.1 Justification of sample size

The study will include patients with a clinically confirmed diagnosis of ARVI (ICD-10 code: J00, J02, J04, J06), who will be randomized and distributed to one of two groups in a 1:1 ratio: Group 1 - patients who will be prescribed the study product as part of complex therapy; Group 2 - patients who will be prescribed a placebo as part of complex therapy.

A similar study of the efficacy, tolerability and safety of Polyoxidonium® in children with acute respiratory infections [5] involved 98 patients (52 in the group of the study product and symptomatic therapy, 46 in the placebo group and symptomatic therapy). The duration of fever and intoxication in the group of the study product was 2.6 ± 0.2 days, in the placebo group - 3.2 ± 0.2 days. Thus, the superiority of the efficacy of the drug Polyoxidonium® over the efficacy of a placebo in relation to the duration of the period of fever and intoxication was $-0,60 [-0,68; -0.52]$ days; the upper limit of the 95% confidence interval for the difference in efficacy of the study product and placebo was -0.52 days. Data from another study, in general, confirms the indicated efficacy values: in children who received Polyoxidonium® in the complex of therapy, compared with children who received only macrolide drugs, their body temperature decreased by 1-2 days earlier, shortness of breath, coughing, wheezing in the lungs (Kuzmenko L.G. The use of Polyoxidonium® in the treatment of frequently ill children, "EFFECTIVE PHARMACOTHERAPY. Pediatrics, No. 2, 2013).

In this study, the fever duration and intoxication period were selected as the main parameter characterizing the efficacy of the therapy. Value of $\delta = -0.52$ days is considered as the margin of excellence.

Calculation of the sample size is based on the following formula:

$$n = (Z_{\alpha} + Z_{\beta})^2 \cdot \frac{2 \cdot SD^2}{(\mu_o - \mu_p - \delta)^2}$$

where, Z_{α} and Z_{β} are critical values of the normal distribution corresponding to the established error levels α and β (α - and β -errors are 0.05 and 0.2, respectively), SD - a standard deviation [25 - 28].

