As a result of calculation based on the above values ($Z\alpha=1.645$, $Z\beta=0.842$, $SD=0.2$ day, $\delta=-0.52$ day, $\mu_o=2.6$ days, and $\mu_p=3.2$ days), the sampling size was obtained that ensures a statistical study power of at least 80%, equal to 78 patients in each group (156 subjects in total). Taking into account the dropout of patients at screening, it is planned to obtain Permission of the Ministry of Health of the Russian Federation to screen 210 patients, of whom 172 will be randomized.

Patients enrolled in the study will be randomized to one of two groups using Polyoxidonium® or placebo.

12.2 Description of the statistical methods to be used, including terms of each interim analysis

Given the main study purposes (efficacy and safety assessment), the main tools for the analysis will be descriptive statistics and graphical representations.

Continuous (quantitative) variables will be tabulated using such parameters of summary statistics as the amount of data, the amount of missing data, mean, standard deviation, median, Q_1 and Q_3 , minimum and maximum values.

The descriptive statistics and tables will be presented for all demographic and baseline data. Baseline demographic characteristics, medical history and examination data are the most recent data recorded before the first product use. A comparative analysis of these data will be carried out in a population of patients who have undergone all the study procedures and completed it according to the Protocol (per-protocol (PP) population). Based on the results of efficacy analysis, the comparative statistics will be presented. Comparison of quantitative indicators satisfying the conditions of normal distribution and equality of variances will be carried out by Student's t-test. Comparison of quantitative indicators not satisfying the conditions of normal distribution and equality of variances will be carried out by Mann-Whitney test. To compare the paired quantitative indicators satisfying the conditions of normal distribution and equality of variances, the paired Student's t-test will be used; for those not satisfying the conditions of normal distribution or equality of variances - the paired Wilcoxon test. A comparative analysis of qualitative variables will be carried out by Chi-square test; if more than 20% of the expected frequencies are less than 5, the exact Fisher's two-tail test will be used.

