12.3 Efficacy data analysis

A superiority cut-off level $\delta = -0,52$ days was chosen to evaluate the principal efficacy parameter - fever duration. The choice is based on the results of earlier studies, which evaluated fever duration in similar cohorts of patients [4, 5].

Therein, the following statistical hypotheses will be verified:

- **Null-hypothesis (H_0):** efficacy of the study product does not exceed the efficacy of placebo:

$$H_0: \mu_o \geq \mu_p + \delta,$$

where, μ_o and μ_p - average fever and intoxication period in the main group (μ_o) and placebo group (μ_p);

- **Alternative hypothesis (H_A):** therapy with the study product is better than placebo therapy:

$$H_A: \mu_o < \mu_p + \delta$$

A comparison of parameters between two groups of patients can be performed by calculating the 95% confidence interval for the difference between μ_o and μ_p . Efficacy of the study product is considered higher compared with the efficacy of placebo, if the upper limit of 95% confidence interval for the difference between μ_o and μ_p values is less than - (minus) 0.52 days.

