12.5 Applicable level of significance

The statistical hypothesis will be verified at a 5% significance level, indicating the corresponding two-sided 95% level confidence intervals (or one-sided 97.5% confidence intervals).

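### No covariate adjustment is prespecified for fever duration, although baseline temperature, symptom score and age are recorded before the first dose; the confidence interval is probably wider than necessary

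*Combined protocol and SAP*

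**What the plan says.** **Method.** Section 12.2 states: "Comparison of quantitative indicators satisfying the conditions of normal distribution and equality of variances will be carried out by" Student's t-test. Mann-Whitney replaces it when those conditions fail.

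**Decision rule.** Section 12.3 proposes "calculating the 95% confidence interval for the difference between" the two group means. Success is declared "if the upper limit of 95% confidence interval for the difference between" them lies below −0.52 day. Section 12.5 describes the intervals as "indicating the corresponding two-sided 95% level confidence intervals (or one-sided 97.5% confidence intervals").

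**Covariates.** Sections 12.2 to 12.5 name no covariate, regression model or stratified analysis. The protocol names no stratification factor for randomisation either; section 7.3.2 leaves the scheme to a separate document.

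**What is recorded before the first dose.**
- Body temperature and the Symptom Assessment Scale, at Visits 0 and 1 (sections 9.1.1 and 9.1.2, Appendix 5).
- Date of birth and "age (number of full years at the time of participation in the study") (section 9.1.6). Age also sets the dosing band (section 7.4).
- Disease duration, without units (section 9.1.1), and "date of disease onset" (section 11.1).

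**Room for later detail.** The opening of section 12 defers final methods to a more detailed statistical document. The end of section 12.4 allows methods to be added after data collection. Neither mentions adjustment.

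**The concern.** The trial admits children from 1 to 12 years with an axillary temperature from 37.0 °C to just under 40 °C (sections 8.1 and 8.2). The endpoint is time until temperature is down to 36.9 °C or below on two consecutive readings, so a child's starting temperature is a natural candidate to predict it. Section 5.8 points the same way. It describes onset as often subfebrile, associates higher fever with certain viruses, and says that two of these, influenza and adenovirus, have longer fevers. Influenza is screened out by express test; adenovirus is not. The same section describes presentation as differing with age.

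An unadjusted comparison leaves any variance explained by these values in the error term. Interval width matters here because the planned difference of −0.60 day lies only 0.08 day beyond the limit of −0.52.

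Timing matters too. If covariates are not fixed in advance, the freedom in section 12.4 to add methods after data collection would make a later adjusted result hard to credit.

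**Working it through.** **Inputs from the documents (sections 12.1, 12.3 and 12.5).** Means 2.6 and 3.2 days; limit −0.52 day; SD 0.2 day; "errors are 0.05 and 0.2, respectively" for α and β; Zα = 1.645; Zβ = 0.842; 78 evaluable children per group.

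**Assumed.** R², the share of variance in fever duration explained by the covariates, is not given. A range of 0 to 0.30 is shown.

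**1. The plan's own figure.** The gap is |2.6 − 3.2 + 0.52| = 0.08 day. Then n = (1.645 + 0.842)² × 2 × 0.2² / 0.08² = 77.3, so 78 per group. The stated figure reproduces, with no covariate gain built in.

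**2. Unadjusted interval.** SE = 0.2 × √(2/78) = 0.0320 day. The 95% half-width is 1.96 × 0.0320 = 0.0628 day.

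**3. Effect of adjustment on width.** The residual SD becomes SD × √(1 − R²). Five covariate degrees of freedom are charged: temperature 1, four age bands 3, and one more such as baseline symptom score. With N = 156 and k = 5:

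- allowance for estimating the covariate effects: √(1 + k/(N − k − 3)) = √(1 + 5/148) = 1.0168;
- ratio of t quantiles on 149 and 154 degrees of freedom: 1.9760 / 1.9755 = 1.0003;
- adjusted width / unadjusted width = √(1 − R²) × 1.0168 × 1.0003 = √(1 − R²) × 1.0170.

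| Assumed R² | √(1 − R²) | Width ratio after df cost | Change in CI width |
|---|---|---|---|
| 0 | 1.000 | 1.017 | 1.7% wider |
| 0.05 | 0.975 | 0.991 | 0.9% narrower |
| 0.10 | 0.949 | 0.965 | 3.5% narrower |
| 0.20 | 0.894 | 0.910 | 9.0% narrower |
| 0.30 | 0.837 | 0.851 | 14.9% narrower |

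Break-even: 1 − 1/1.0170² = 0.033. These ratios do not depend on the SD.

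**4. Power, conditional on SD 0.2.** Under the two-sided 95% rule, power = Φ(0.08 / (0.0320 × ratio) − 1.96).

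- Unadjusted: Φ(2.498 − 1.96) = 70.5%.
- Adjusted, ignoring the df cost: 75.0%, 79.8% and 84.7% at R² 0.1, 0.2 and 0.3.
- Adjusted, with the df cost: 69.0%, 73.5%, 78.4% and 83.5% at R² 0, 0.1, 0.2 and 0.3.

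The 70.5% starting point is not caused by the missing covariates. It arises because the sample size uses one-sided 1.645 while the decision uses 1.96; planning on the latter gives 99 per group.

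**5. Sensitivity to the SD.** At an assumed SD of 1.0 day, 78 per group gives 7.2% power unadjusted and 8.5% at R² = 0.3 after the df cost. The relative narrowing is the same, but the gain in power almost vanishes.

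**The case against.** The strongest case on the other side has five parts.

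- **An unadjusted comparison is valid.** Under randomisation, leaving out covariates does not bias the difference, and nothing in the documents is contradicted. This stands. A reader might infer that the planned analysis is wrong or biased; the documents do not support that. Efficacy is analysed per protocol only, so randomisation does not guarantee balance in the analysed set, but that concern belongs to the choice of population.
- **The gain is not established.** No R² is given. A reader might infer that the interval is certainly too wide; the documents support only probably. Section 5.8 ties fever length to the virus and only indirectly to entry temperature. If the covariates explain less than about 3% of the variance, adjustment slightly widens the interval.
- **Power figures look firmer than they are.** They need an SD of 0.2 day, which is doubtful for an endpoint built from twice-daily readings in children aged 1 to 12. A reader might also infer that adjustment restores 80% power. After the df cost it does not at R² 0.2, and the shortfall comes from the one-sided/two-sided mismatch.
- **Time since onset may not be usable.** Section 11.1 names a date and section 9.1.1 a duration without units, and eligibility caps it at 24 hours. The documents do not show that hours from onset are recorded.
- **Fever duration may be coarse and skewed.** The plan itself provides for Mann-Whitney. This bears on how the linear model's standard errors are obtained. It does not rule out adjustment, since the decision rule in 12.3 is already about a difference in means.

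**Conclusion.** The point holds as a modest, low-cost improvement in precision. The primary comparison is unadjusted, and baseline temperature, symptom score and age are recorded in time to be used. The interval is probably wider than necessary.

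The trade is asymmetric: at worst a loss of about 2% in width, against a possible gain of up to about 15% over the assumed range of R². Confidence is high that adjustment is not prespecified, and moderate at most on how much it would gain. The relative figures rest on the assumed R² and on about 5 covariate degrees of freedom; the absolute power figures rest in addition on the SD of 0.2 day. Adjustment is no remedy for a doubtful SD or for the one-sided/two-sided mismatch, which need their own correction.

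**What to change.** In section 12.3, or in the later statistical document but before unblinding:

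- Make the primary analysis a linear model of fever duration on treatment, with baseline axillary temperature (last value before the first dose) and age band as covariates. Baseline symptom score is optional. Include time since onset only if it is recorded in hours.
- Compare the adjusted mean difference and its two-sided 95% confidence interval with the stated limit. Name robust or bootstrap standard errors for use if residuals are skewed.
- Keep the unadjusted comparison as a sensitivity analysis.

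Cost: one paragraph, with no new patients and no new data for the covariates named. The downside is a few degrees of freedom and an interval up to about 2% wider if the covariates are not prognostic.

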	
A superiority cut-off level $\delta = -0,52$ days was chosen to evaluate the principal efficacy parameter - fever duration. The choice is based on the results of earlier studies, which evaluated fever duration in similar cohorts of patients [4, 5].
 
Therein, the following statistical hypotheses will be verified:
 
- Null-hypothesis (H_0): efficacy of the study product does not exceed the efficacy of placebo: $H_0: \mu_o \geq \mu_p + \delta$, where, μ_o and μ_p - average fever and intoxication period in the main group (μ_o) and placebo group (μ_p);- Alternative hypothesis (H_A): therapy with the study product is better than placebo therapy: $H_A: \mu_o < \mu_p + \delta$ 
A comparison of parameters between two groups of patients can be performed by calculating the 95% confidence interval for the difference between μ_o and μ_p. Efficacy of the study product is considered higher compared with the efficacy of placebo, if the upper limit of 95% confidence interval for the difference between μ_o and μ_p values is less than - (minus) 0.52 days.
 
Safety data analysis
 
Safety population will be evaluated for all types of safety analysis. Preferred terms of MEDDRA dictionary (Preferred Term) will be used for coding and presenting the Lists of adverse events and associated diseases. All adverse events in the aggregate, as well as serious adverse events, adverse events associated with the therapy, and on other significant adverse events (for example, on adverse events that led to the cancellation of study therapy) will be presented through descriptive statistics.
 
Comparison of treatment groups by the incidence of AEs will be carried by Fisher's exact test.
 
Clinical laboratory evaluations together with indication of changes from baseline will be presented through descriptive statistics for each visit. Laboratory deviations beyond normal values will be marked. Lists and summary descriptions of clinically significant hematological laboratory abnormalities will be presented.

--	---

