10. EFFICACY ASSESSMENT

In this study, the efficacy will be assessed based on the body temperature changes recorded in the patient's diaries at home by the parent / adoptive parent of the child; based on the Symptom Assessment Scale, IMOS scale, evaluation of the efficacy of the patient's parent / adoptive therapy, the number of cases of consumption of the antipyretic drug, the number of cases of dropout of patients due to the need to prescribe antibacterial drugs.

The multiplicity and rules for the use of these diagnostic scales are described in detail in the protocol section 9.2 "Diagnostic scales and Patient's diary".

Primary efficacy criterion:

- Fever duration period³ $\delta = -0.52$ days will be considered as a superiority cut-off level. Axillary body temperature level ≤ 36.9 °C confirmed by two consecutive measurements (morning-evening/evening-morning) will be considered as the end of fever.

Secondary efficacy criteria:

- The dynamics of intoxication symptoms by Days 3, 8 of treatment, assessed according to the Symptom Assessment Scale .
- Assessment of the ongoing therapy efficacy by a physician at the end of treatment course (IMOS scale) - complete recovery (0 points), significant improvement (1 point), minor to moderate improvement (2 points), unchanged (3 points), worsening (4 points).
- Assessment of the ongoing therapy efficacy by the patient's parent/adoptive patient (excellent, good, satisfactory, not efficient) - scores from 0 to 3.
- Number of cases of the antipyretic product (paracetamol) consumption for the entire study period.
- Number of patients' dropout patients due to the need to prescribe the antibacterial products.
- Number of patients (%) with body temperature normalization (presence of axillary body temperature ≤ 36.9 °C in two consecutive measurements (morning-evening/evening-morning) on Day 5 of therapy.
- Number of patients (%) with clinical pattern normalization on Day 5 of therapy according to the Symptom Assessment Scale (total ≤ 3 points).

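### The plan does not exempt fever duration from the margin-free t-test/Mann-Whitney rule in 12.2, so the −0.52-day interval rule in 12.3 should be declared the single primary analysis

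*Combined protocol and SAP*

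**What the plan says.** **The specific rule.** Section 12.3 (repeated in the Synopsis) states hypotheses on the average duration in each group, with δ = −0.52 days inside H0. It introduces the method permissively: "A comparison of parameters between two groups of patients can be performed by calculating the 95% confidence interval for the difference". The success rule that follows is definite: "Efficacy of the study product is considered higher compared with the efficacy of placebo, if the upper limit of 95% confidence interval" for the difference is below −0.52 days. The method of building the interval is not named. Section 12.5 adds that the hypothesis is verified at the 5% level with two-sided 95% (or one-sided 97.5%) intervals. The threshold is also written into the primary criterion in Sections 7.1 and 10 ("days will be considered as a superiority cut-off level") and into the sample size in 12.1 ("days is considered as the margin of excellence").

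**The general rule.** Section 12.2 (also repeated in the Synopsis) opens its comparative part with "Based on the results of efficacy analysis, the comparative statistics will be presented". It then directs, in mandatory wording, "Comparison of quantitative indicators satisfying the conditions of normal distribution and equality of variances will be carried out by Student's t-test" and, for the other case, "Comparison of quantitative indicators not satisfying the conditions of normal distribution and equality of variances will be carried out by Mann-Whitney test". Neither sentence mentions a margin. Neither sets fever duration apart from other quantitative efficacy measures.

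No sentence says that 12.3 overrides 12.2 for the primary endpoint, or what standing a 12.2 test of fever duration would have.

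**The concern.** Fever duration is a quantitative efficacy measure, so taken literally 12.2 applies to it. The analyst would then look at the data, decide whether normality and equal variances hold, and run one of two tests. Under 12.3 the analyst compares a confidence limit for a difference in means with −0.52 days. These are different questions.

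Mann-Whitney compares whole distributions. Even if it were shifted by 0.52 days, it would answer the question about means only where the two distributions share a shape. Student's t-test does concern means, but 12.2 names no null value, and the customary one is zero.

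Section 12.3 also glosses H0 in words as the product being no better than placebo. A reader could match that to a test against zero, although the formula carries the margin.

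If a favourable 12.2 test were presented as the primary result, the error rate for the stated H0 would not be controlled.

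**Working it through.** **1. The plan's own figure.** Inputs from 12.1: Zα = 1.645, Zβ = 0.842, SD = 0.2, means 2.6 and 3.2, δ = −0.52.

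n = (1.645 + 0.842)² × 2 × 0.2² / (2.6 − 3.2 + 0.52)² = 6.185 × 0.08 / 0.0064 = 77.3, rounded up to 78 per group, as stated.

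This is a formula for a difference in means against the margin, so the trial was sized for the 12.3 rule. (It uses a one-sided 5% value while 12.3 and 12.5 use a two-sided 95% interval. That is a separate matter and is not relied on here.)

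**2. SD values.** The protocol uses 0.2 day. The values 1.0 and 1.4 are assumptions that show the range. The SD would be near 1.4 only if the ±0.2 quoted from the earlier study were a standard error: 0.2 × √46 = 1.36 and 0.2 × √52 = 1.44.

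**3. Observed difference needed, 78 per arm.** With t(0.975, 154) ≈ 1.976 and √(2/78) = 0.160, a t-test against zero needs −1.976 × SD × 0.160. The interval rule needs a further −0.52.

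| SD | t-test against zero | 12.3 interval rule |
|---|---|---|
| 0.2 | −0.06 | −0.58 |
| 1.0 | −0.32 | −0.84 |
| 1.4 | −0.44 | −0.96 |

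**4. Behaviour at the edge of H0 (true difference exactly −0.52).** Normal approximation, SE = SD × 0.160:

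- t-test against zero, probability of favouring the product = Φ(0.52/SE − 1.96). SD 0.2: Φ(14.3), about 100%. SD 1.0: Φ(1.29) = 90%. SD 1.4: Φ(0.36) = 64%.
- Interval rule: Φ(0 − 1.96) = 2.5% at every SD.

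Simulation used 1,500 trials per setting, normal and lognormal durations, and a placebo mean of 3.2 days varied by ±0.25. Duration was counted in three ways (rounded up to half-days, clock-time start with half-day end readings, exact), because the documents fix no start point or rounding rule:

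| Result favouring the product | SD 0.2 | SD 1.0 | SD 1.4 |
|---|---|---|---|
| Mann-Whitney | 100% | 88–95% | 60–81% |
| Student's t against zero | 100% | 88–91% | 61–64% |
| 12.3 interval rule | 1.8–3.6% across all SDs | | |

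Simulation error is about ±0.8 points near 2.5%, so the last row agrees with the nominal 2.5%. Pooled-t and Welch intervals agreed within 0.1 point.

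**5. Covariate adjustment.** The SE falls by 1 − √(1 − R²). For an assumed R² of 10/20/30% that is 1 − 0.949, 1 − 0.894 and 1 − 0.837, or about 5/11/16%. In simulation with half-day readings the gain was somewhat smaller: about 2/6/9% at SD 0.2 and 4/9/15% at SD 1.0–1.4. The documents give no R².

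**The case against.** The best reply is that the specific rule governs the general one. Section 12.3 names fever duration, its hypotheses and its success rule. Section 12.5 ties verification of the hypothesis to a 95% interval. The primary criterion and the sample size carry the same threshold, and no zero-difference hypothesis for fever duration is stated anywhere. The permissive verb in 12.3 carries little weight, since the next sentence is definite. A t-test applied to the only stated H0 is the same thing as a t-based interval compared with −0.52. All of this stands, and it is why the plan is not missing a primary analysis.

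Other safeguards are real but do not close the gap. Statisticians are blinded until database lock (7.3.1), which does not say which result is primary. Section 12 defers detail to a later statistical document, which may settle the point, but the supplied text does not. Section 12.7 requires changes to be identified against the methods in the protocol. As the protocol describes both routes, using either need not count as a change.

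Stronger inferences a reader might draw are not supported:

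- *That the unnamed interval method could by itself decide the trial.* The hypotheses concern averages, so the interval is for a difference in means, and the pooled and Welch forms practically coincide. A Hodges-Lehmann interval addresses a different parameter and is nowhere named.
- *That trials passing a 12.2 test but failing the 12.3 rule prove a defect.* Any trial with a margin beyond zero shows that gap, however well it is written.
- *That the Shapiro-Wilk switch and the open choice of methods in 12.4 govern the primary endpoint.* They stand under the safety heading.

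**Conclusion.** The concern holds in a limited form. The ordinary primary rule is the 12.3 interval for the mean difference against −0.52 days, and under it the chance of a false claim at the edge of H0 is about the intended 2.5%. What remains is that 12.2, followed literally, sends fever duration through a data-dependent switch whose Mann-Whitney branch does not test the stated H0, and whose two tests carry no margin. Read against zero, those tests would favour the product at the edge of H0 in nearly 100% of trials at SD 0.2, and in about 60–95% at the assumed SDs of 1.0–1.4.

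These figures describe a misuse that the text leaves open, not the error rate of the planned analysis. They matter only if a 12.2 result is presented as primary. They rest on 78 analysed per arm, on reading the 12.2 tests against zero (which 12.2 does not state) and, above SD 0.2, on assumed SDs. The change should be made because it removes the ambiguity at almost no cost. Confidence is medium, since a later analysis document may already settle it.

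**What to change.** - **Section 12.3 and Synopsis:** replace the permissive verb with *will be performed*. State that the two-sided 95% confidence interval for the difference in mean fever duration, compared with −0.52 days, is the single primary analysis whatever the normality result. Name one interval method in advance, for example Welch or a linear model with robust standard errors.
- **Section 12.2 and Synopsis:** exempt fever duration from the t-test/Mann-Whitney switch, and label any such test of it supportive.
- **Optional:** fit the primary comparison as a linear model adjusted for baseline temperature (measured at Visits 0 and 1, Sections 9.1.1–9.1.2) and age in full years (9.1.6), with the covariates fixed in advance. The unadjusted analysis is valid without this, and the precision gain is not known from the documents.

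Cost: a wording amendment. Under 14.4 it may count as significant and then needs approval from the ministry and the local ethics committees. It needs no new data, visits or patients.
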